1. BACKGROUND	
2. RATIONALE	
3. THEORETICAL FRAMEWORK	
4. RESEARCH QUESTION/AIM(S)	
5. STUDY DESIGN/METHODS	
6. STUDY SETTING	
7. SAMPLE AND RECRUITMENT	
8. ETHICAL AND REGULATORY COMPLIANCE	
9. DISSEMINATION POLICY	
10. REFERENCES	
11. APPENDICES	

KEY STUDY CONTACTS	
Chief Investigator	[name], Consultant Radiologist, Deputy Research Lead, St George's Hospital
Study Co-ordinator	[name], MRI Annexe St George's Hospital, [name], [name], [contact]
Sponsor	St George's, University Hospitals NS Foundation Trust
	Name: [name]
	Position: Lead Sponsor
	Email: [contact]
	St Georges Joint Research & Enterprise Service (JRES), [name]
Funder(s)	St George's Hospital NHS Foundation Trust
Key Protocol Contributors	[name], MRI Annexe St George's Hospital, [name], [name], [contact]
	[name], MRI Annexe St George's Hospital, [name], [name]
	[contact]
	[name], MRI Annexe St George's Hospital, [name], [name]
	[contact]
	[name], Consultant Radiologist, Deputy Research Lead, St George's Hospital
Committees	

STUDY SUMMARY	
Study Title	Quantitative assessment of image quality in rectal cancer MR images when using artificial intelligence reconstruction techniques
Internal ref. no. (or short title)	Assessing the use of artificial intelligence in rectal magnetic resonance imaging
Study Design	Observational clinical study

Protocol Version 0.3 and 29/07/24

Study Participants	Healthy volunteers and patients referred for rectal MRI at St George's Hospital General Radiology MRI Department	
Planned Size of Sample (if applicable)	75	
Follow up duration (if applicable)	N/A	
Planned Study Period	June 2024 – April 2025	
Research Question/Aim(s)	Hypothesis: Al reconstruction techniques can be successfully implemented into the MRI rectal protocol, providing improved image quality and/or reduced acquisition times improving patient outcomes and staff workload.	
FUNDING AND SUPPORT		
FUNDER(S)	This study is unfunded with any resources used in this study volunteered by St George's Hospital's General Radiology MRI department	

Department.

ROLES AND RESPONSIBILITIES OF STUDY MANAGEMENT COMMITEES/GROUPS & INDIVIDUALS

Study Steering Groups

This section details the members of the steering group who are responsible for coordinating and the conduct of this study.

[figure not shown]
Trial Steering Group		

1 BACKGROUND

Aim: This study aims to assess the influence of Deep Learning Reconstruction (DLR) techniques on rectal cancer MR images and the patient pathway. National implementation of DLR techniques was initiated to combat COVID-19 backlogs (GOV.UK, 2023) and can maintain or increase MRI image quality while decreasing acquisition time. While this improves the clinical service by reducing waiting times and increases patient comfort, the use of DLR for rectal cancer imaging is yet unvalidated and must undergo qualitative and quantitative assessment. This is crucial for rectal cancer imaging as tumour size must be accurately determined as this is a biomarker for rectal cancer staging (Horvat et al, 2019).

Literature Review: As a Cancer Centre, St George's University Hospitals NHS Foundation Trust treats patients with colorectal cancer in Southwest London and hosts various screening programs, including that for colorectal cancer (St George's University Hospitals NHS Foundation Trust, n.d.). Colorectal cancer surgery is performed at St George's and among the methods of identifying and staging colorectal cancers include MR imaging (St George's University Hospitals NHS Foundation Trust, n.d.). However, waiting times for patients referred to St George's for treatment for colorectal cancer are currently at 15 weeks (about 3 and a half months), and waiting times for a patient's first outpatient appointment is as high as 16 weeks (My Planned Care NHS, n.d.). Guidance from NHS England state that there should be a maximum of two months (62 days): "From receipt of an urgent GP (or other referrer) referral for urgent suspected cancer or breast symptomatic referral, or urgent screening referral or consultant upgrade to First Definitive Treatment of cancer" (NHS England, 2023). While colorectal cancer is considered a slow-progressing cancer, it was found to be the second highest in cancer-related deaths overall and ranks as the second highest cause of death in men younger than 50 years old in the US (Siegel et al. 2023). Overall survival is closely dependent on early detection: 5year overall survival is 95-100% for Stage I cancer and drops to 7-8% for stage IV cancer ([name], n.d.).

While various methods of staging rectal cancer exist (pathological staging and contrast-enhanced CT), MRI is crucial for rectal cancer staging. NICE guidelines mandate high-resolution MRI imaging of the rectum in the UK for the identification of metastatic disease (NICE, 2022). Imaging determines the patient pathway and patient treatment based on detectable tumour features visible in MRI ([name], n.d.). Various markers are used by reporters to identify and stage rectal cancer, including the extension of the tumour through the bowel wall, the detection of the circumferential resection margin, detection of extramural vascular invasion, the assessment of nodal status and extranodal tumour deposits, as well as tumour height ([name]). MRI is capable of achieving all of these and has the benefit of being non-invasive and does not include exposing the patient to ionising radiation.

While specific protocols naturally vary between hospitals, the current clinical standard for rectal MRI includes a T2-weighted turbo spin echo (TSE) without fat saturation from the aortic bifurcation to the sphincter, with a small field-of-view (FOV) oblique and a large FOV axial and sagittal image as a minimum. This allows for the localisation of the primary tumour (Horvat et al, 2022). Other sequences that could be added include diffusion-weighted imaging (DWI), 3D T2-weighted imaging, contrast-enhanced T1-weighted imaging (Horvat et al, 2019). At St George's, the basic rectum protocol includes a T2w TSE sagittal (for planning), a T2w TSE axial of the whole pelvis, and T2w TSE coronal and axial obliques (with small FOV in the plane of the tumour). Including the localiser, this basic protocol can take over 20 minutes. Further protocols could be added which could provide more diagnostic information for

radiologists (eg. DWI to support localisation, imaging of the nodes to assess cancer spread), however this would cause an increase in scan duration. Long scan times are one of the main drawbacks of MRI in general as patient discomfort, anxiety and claustrophobia can deter patients from being scanned.

In 2023, the UK government rolled out artificial intelligence (AI) tools across the NHS to combat waiting times, which had increased drastically after the peak of the COVID-19 pandemic (GOV.UK, 2023). This included Siemens' Deep Resolve Boost technology, a deep learning image reconstruction (DLR) technology used in MRI (Siemens Healthineers, n.d.). DLR reconstructs MR images from undersampled k-space data with image quality comparable to that obtained from a fully sampled data set (Linetal, 2023). To convert raw k-space data to image space, a Fourier transform is performed on k-space data, which contains frequency and phase information. In DLR, the Fourier transform is first performed on zero-filled k-space data to produce an aliased image, then uses training data to map the aliased image to the to the reconstructed image via a convoluted neural network (CNN) (Linetal, 2023). Because k-space is not sampled completely, this decreases scan time, which benefits the patient experience and increases efficiency of throughput through the MRI department.

In conventional imaging acceleration techniques, there is a known trade-off between acquisition time and signal-to-noise ratio. However, in DLR imaging, noise maps are used which are acquired with the raw data directly into the image reconstruction through iterative techniques, providing clear depiction of fine structures and edges (Magnetom Flash, 2021). DLR denoising techniques allow more effective denoising without increasing scan time.

The combined improvements in scan time and image quality make DLR technology a promising tool to improve patient experience and throughput within the MRI department at St George's, particularly in Rectal MRI where fine soft tissue boundaries and structures play a key role in diagnosis and staging, and decreasing scan time could allow for more sequences to be added to the protocol which can provide more diagnostic information for the reporters and decrease patient recalls.

Although a relatively new technology, studies are emerging on the effectiveness of DLR in MRI not only in decreasing scan time but also in improving image quality. Brix et al. found that in a three-month trial, procuring DLR shortened patient scans allowed the hospital to sustain current MRI service levels with one fewer scanner, enabling a 399,000EUR cost saving annually (Brix et al, 2024). In terms of image quality, Zerunian et al. concluded that signal-to-noise ratio (SNR) and contrast-to-noise ratio (CNS) were both higher in DLR images compared to conventional imaging in a blinded Likert scale assessment scored by radiologists. Furthermore, higher image quality could also be achieved while simultaneously shortening the total protocol scan time from 12:59 minutes to 6:26 minutes (Zerunian et al, 2023).

However, DLR technology cannot be implemented on rectal cancer MRI without thorough validation to assess feasibility. DLR algorithms are known to be a 'black box', where their failure modes are not well understood (Lin et al, 2023). There have also been cases where abnormalities on the fully sampled images have not been visualised on deep learning-reconstructed images (Knoll et al 2020). Therefore, the use of DLR in rectal cancer imaging must be thoroughly validated and feasibility assessed before implementation into the clinical protocol. This will require the participation of volunteers and patients who have been referred for an MRI pelvis scan for a rectum study.

2 RATIONALE

One of the disadvantages in MRI is that acquisition times can be lengthy, making it likely that patient movement whilst in the scanner will affect image quality and making it more difficult for patients to complete their MRI scan (Hollingsworth et al. 2015). In recent years, waiting lists of patients referred for MRI have also been at an all-time-high as a result of the COVID-19 pandemic (GOV.UK, 2023).

To tackle this backlog, manufacturers have developed Artificial Intelligence (AI) image reconstruction (DLR) techniques that compensate for the poor image quality that results when using higher accelerating/parallel imaging factors during MRI scanning (Magnetom Flash, 2021). This also has the potential to improve patient compliance.

These DLR techniques are still relatively new and require a number of resources including radiographer, radiologist and clinical scientist support to optimise the technique. Consequently, implementation across the NHS has been slow and has therefore not yet been validated on rectum MRI protocols. Therefore, the aim of this study is to demonstrate that DLR techniques can be implemented in rectum MRI protocols, as well as provide recommendations for its implementation.

3 THEORETICAL FRAMEWORK

MRI is the gold standard for imaging rectal disease with much discussion in the literature regarding the ideal imaging protocol. The pre-existing clinical rectum MRI protocol at St George's Hospital consists of several T2-weighted Turbo-Spine Echo (TSE) sequences to visualise the primary tumour, the surrounding tissue/organs as well as local nodes. This is in agreement with the literature (Pizzi et al., 2018).

Following the initial imaging, the patient will follow a complex pathway with multiple strategies including neo-adjuvant chemo-radiotherapy, surgery, adjuvant chemo-therapy, watch-and-weight, follow-up imaging or no follow up imaging ([name]). The path selected by the clinicians is dependent on the biomarkers measured within the T2-weighted images.

Currently, DLR techniques for the MRI scanners within St George's Hospital's General Radiology department can only be used with Turbo Spin-Echo (TSE) sequences and though it has the potential to reduce acquisition times, it must be validated to ensure it can produce equivalent image quality and biomarker measurement accuracy. All sequences enabled with DLR techniques will be used in accordance with their CE marking. The assessment will involve radiologists, as suggested by the manufacturer, completing Likert scoring assessments, which are common in projects that assess image quality (Mantiuk et al, 2012).

4 RESEARCH QUESTION/AIM(S)

Aims of the project:

This local validation project aims to explore the use of DLR techniques in clinical rectum MRI studies. This will also involve assessing the outcomes to patients referred for these types of scans, as well as for staff involved in the patient pathway (radiographers and radiologists).

4.1 Objectives

Primary Objectives:

- i) Create a DLR enabled MRI Rectum protocol that has equivalent or better image quality as the pre-existing clinical protocol with support from radiographers and radiologists.
- ii) Image volunteers using the DLR protocol and iteratively review and re-optimise, if necessary, with radiologist input.
- iii) Validate the DLR protocol on clinical MRI rectum studies.

4.2 Outcome

Primary outcome:

To demonstrate non-inferiority of the DLR enabled MRI rectum technique to the current clinical protocol by:

a. Following a reduction in the acquisition time equivalent image quality is achieved (by Likert score – Median likert score DLR enabled >= clinical)

Secondary outcomes:

- a. To show agreement between the clinically relevant measurements of rectal tumours on DLR enabled vs clinical scans
- b. To describe the potential benefits of using DLR enabled protocols, including shortened acquisition times and improved imaged quality.

5 STUDY DESIGN and METHODS of DATA COLLECTION AND DATA ANALYIS

Radiographers, radiologists and physicists together will optimise the initial rectum protocol with DLR techniques enabled on healthy volunteers in the initial outset. Images will be pseudo-anonymised/anonymised and stored on the trust's Patient Archiving and Communications System (PACS) by the scanning radiographer. Data that can be used to identify the healthy volunteers will be stored in a locked spreadsheet behind the trust's firewall. This can be used to identify a volunteer whose images contain an incidental finding.

Volunteer images will be viewed on PACS, and a qualitative image quality assessment will be performed using a Likert scoring assessment undertaken by Consultant Radiologist [name]. The Likert scoring form includes scores for image quality (signal-to-noise ratio, overall image quality), and assessment of anatomical features (rectal wall, muscle fibres, intersphincteric plane and myentric plexus) as well as an overall assessment of whether or not the radiologist agrees the image is of adequate quality to report. The likert scale also includes an assessment on bowel motion. These scores will be documented on paper and stored in a locked cabinet in the medical physicists' office (MRI Annexe - ground floor) that is secured with coded pin access. These scores will contain a code to link the scores with the images acquired. No information that can be used to identify the volunteers will be recorded on these documents.

Any images that are accessed in order to perform image quality measurements e.g. SNR, will be done so by MRI physicists ([name] and [name]). The images will be anonymised/pseudo-anonymised and exported from PACS to a trust terminal so that the anonymised/pseudo-anonymised images remain behind the trust firewall. Image quality metrics will also be calculated using an in-house Matlab 2022b script written by MRI physicists ([name] and [name]).

Once a DLR enabled rectum protocol has been established, patients who meet the inclusion criteria will be invited to take part in this study. If they give informed written consent, their routine scans will be appended with the DLR sequences. A maximum of 15 mins of sequences will be added. Their participation in this study will be noted on the trust's Radiology Information System (RIS)/Soliton. Further detail relating to the inclusion and exclusion criteria for participants can be found in section 7 of this study protocol.

Acquired images will be archived to PACS by the scanning radiographer and will undergo qualitative assessment, the same Likert scoring employed with the healthy volunteers, by [name]. Again, these scores will be documented on paper and stored in a locked cabinet in the medical physicists'

office that is secured with coded pin access. These scores will contain a code to link the scores with the images acquired. No information that can be used to identify the patients will be recorded on these documents. Statistical analysis of the Likert scores will be carried out using a two-tailed pairwise Wilcoxon signed-rank test.

Additionally, bio-marker measurements will also be carried out by the reporting radiologist with statistical analysis of the bio-marker measurements between the pre-existing and DLR enabled sequence for the patient sample group also performed by the MRI physicists ([name] and [name]).

Conclusions regarding image quality and the validity of DLR being suitable for clinical rectum protocols will be made by [name], [name] and [name].

Any other hard copies of data/notes will be stored in the locked cabinet within the locked medical physicists' office.

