7.2 Sampling

7.2.1 Size of sample

We aim to recruit a maximum of **75** participants in this study, which includes **15** healthy volunteers and **60** patient participants (see GPower calculation below).

GPower 3.1.9.7 was used to undertake a power analysis calculation by selecting a Wilcoxon signed-rank test (matched pairs), with the following inputs:

- Two tails
- Normal distribution
- Large effect size (dz) of 0.8
- A error probability of 0.05
- Power (1-β error probability) of 0.95

This results in a sample size of 24.

However, the actual number of patient participants required will be different to the sample size calculated by GPower as it is dependent on how effective DLR techniques are at reducing acquisition times.

A conservative estimate for the reduction in the total acquisition time is approximately 50%. Since the routine protocol is 23 minutes and 57 seconds, decreasing the acquisition time by 50%, and considering only the sequences that can have DLR techniques enabled, results in a DLR enabled protocol of 11 minutes and 46 seconds.

However, as the rectum MRI booking slot is a maximum of 30 minutes, the routine and DLR enabled protocol, which combined is 35 minutes and 43 seconds, cannot be acquired in one booking slot. Therefore, the first half of the DLR enabled protocol will need to be appended to 24 patient participant scans and the second half of the DRL enabled protocol will need to be appended to another 24 patient scans. Increasing or exceeding the minute booking slot cannot be exceed (as stipulated by [name] (Superintendent of General Radiology MRI).

Additionally, patient participants may drop out of the study, whilst other patients may have to be excluded following their scan. An example of the latter may be that the patient had significant movement in the DLR enabled scan, which did not occur during the routine part of the scan. This dropout rate is estimated to be **20%**, as indicated by [name] (Superintendent of General Radiology MRI).

The need to double the number of participants due to logistical factors related to the booking slot, a dropout rate of 20%, as well as the need to scan approximately 3 volunteers results in an estimated maximum sample size of 75 participants:

 $((24 \times 2) \div (1 - 20\%)) + 15 = 75$ participants.

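### Non-inferiority is judged by a comparison of sample medians with no margin or confidence bound, and the Wilcoxon test is not tied to that conclusion

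*Protocol*

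**What the plan says.** Protocol section 4.2 sets the primary outcome as "To demonstrate non-inferiority of the DLR enabled MRI rectum technique to the current clinical protocol". The single item beneath it says that, after the acquisition time is cut, "equivalent image quality is achieved", and gives the criterion in brackets: "Median likert score DLR enabled >= clinical".

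Section 5 fixes the analysis: "Statistical analysis of the Likert scores will be carried out using a two-tailed pairwise Wilcoxon signed-rank test".

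Section 7.2.1 sizes the study for that same test, by "selecting a Wilcoxon signed-rank test (matched pairs), with the following inputs": two tails, "Normal distribution", "Large effect size (dz) of 0.8", alpha 0.05 and power 0.95. This gives 24 pairs. The number is doubled because each patient receives only half of the DLR protocol, then inflated for 20% dropout to 60 patients. With 15 volunteers the total is 75.

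The protocol states no non-inferiority margin and no confidence bound. It does not say what a significant or a non-significant Wilcoxon result would mean for the primary claim.

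**The concern.** A non-inferiority claim needs two things: a largest acceptable loss, and evidence that the true loss is smaller than that. The rule in section 4.2 has neither. It compares two sample medians, ignores the pairing and takes no account of sampling error. Likert scores are coarse and tie heavily, so the median can stay put while a sizeable share of patients is scored lower.

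The test in section 5 asks a different question, namely whether the scores differ. Because the protocol does not connect the two, one data set can meet the success rule while the planned test shows DLR significantly worse, with nothing to say which prevails.

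This matters because the background section cites abnormalities that were visible on fully sampled images but lost on deep-learning reconstructions. The study's conclusions on the suitability of DLR for clinical rectum protocols are to be drawn from these data. An undetected loss is the error that the primary criterion most needs to control.

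This is not detail left to a SAP. The protocol itself fixes the success rule, the test and the sample size. A SAP that followed it would inherit the problem, and one that repaired it would have to depart from section 4.2.

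**Working it through.** **1. The plan's own sample size.** Inputs from section 7.2.1: dz 0.8, two-sided alpha 0.05, power 0.95, normal parent. For the Wilcoxon test under a normal parent, the effective sample size is n × 3/π.

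- Effective n = 24 × 3/π = 22.92, so df = 21.92 and the critical t is 2.074.
- Noncentrality = 0.8 × √22.92 = 3.83, giving power 0.955.
- 24 × 2 / (1 − 0.20) = 60, and 60 + 15 = 75.

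The figures 24, 60 and 75 all reproduce. They belong to a test for a difference. The 0.8 is a difference to detect and is not stated as a tolerable loss.

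**2. Can the median rule be met when DLR is systematically lower?** The protocol does not give the number of Likert points, so a 5-point scale is assumed. Take 24 pairs.

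- Clinical: 8 fives, 14 fours, 2 threes. The 12th and 13th ordered values are 4, so the median is 4.
- DLR: one point lower in ten patients (four of the fives and six of the fours), higher in none. This gives 4 fives, 12 fours and 8 threes, and the median is again 4. The rule is met.
- Mean paired difference = −10/24 = −0.42.
- Wilcoxon: ten non-zero differences, all negative and tied. W+ = 0, expected value 10 × 11/4 = 27.5, and tie-corrected variance (10 × 11 × 21)/24 − (10³ − 10)/48 = 96.25 − 20.625 = 75.625. Then z = −27.5/8.696 = −3.16 and p = 0.0016 against DLR.

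**3. How often could this happen?** Simulation with 24 pairs on the same assumed scale, DLR one point lower in 30% of patients and one point higher in 5% (mean difference about −0.26):

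- Clinical scores 2/3/4/5 in 5/15/60/20%: the rule is met in 86% of trials. In 51% it is met while the Wilcoxon is significantly against DLR.
- Over other assumed clinical distributions: the rule is met in about 55-95%, and both occur together in about 29-63%.

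With 30% lower and none higher, over four assumed distributions, the rule is met in 46-98% of trials. The direction is stable; the percentage is not.

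**4. Would a non-significant Wilcoxon fill the gap?** The protocol does not say that it would be used this way. If it were, the formula in step 1 with 24 pairs gives these probabilities of p ≥ 0.05:

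| True DLR deficit (dz) | Non-significant |
|---|---|
| 0.3 | 72% |
| 0.4 | 55% |
| 0.5 | 37% |
| 0.6 | 22% |
| 0.8 | 4.5% |

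**5. What do 24 pairs per half give for a real non-inferiority test?** Assumptions: one-sided alpha 0.025, true difference 0, margin expressed in SDs of the paired differences. The formula is that of step 1 with the margin in place of dz. Patients = pairs × 2 / 0.8.

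| Margin (SD) | Power, 24 pairs | Pairs per half for 95% | Patients |
|---|---|---|---|
| 0.8 | 95.5% | 24 | 60 |
| 0.6 | 78% | 40 | 100 |
| 0.5 | 63% | 57 | 143 |
| 0.4 | 45% | 88 | 220 |
| 0.3 | 28% | 154 | 385 |

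**The case against.** **A reader might infer that a clearly worse DLR protocol will be declared non-inferior.** The documents do not support that, because without a margin nothing defines clearly worse. The main simulated deficit, a mean of about −0.26, would lie inside a margin of half a point if the radiologists chose one. A confidence-limit rule with that margin would itself pass in about 57% of such trials. What stands is narrower: the rule sets no limit on the loss it lets through, and it can be met when the planned test finds a significant loss.

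**A reader might also infer that a non-significant Wilcoxon result will be taken as proof of non-inferiority.** The protocol never says so. Section 4.2 has one success criterion, the median rule, and section 5 only names an analysis. The figures in step 4 are therefore conditional on a reading that the text leaves open. The fair criticism is that the link is absent.

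**The simulated percentages rest on assumed scales and distributions.** This is correct. They show that the problem is not a rare accident, but no single figure should carry the point. The worked example needs only the assumed 5-point scale and one possible set of scores.

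**There are other safeguards.** Agreement of tumour measurements is a secondary outcome, adequacy to report is scored, and the data protection assessment in Appendix 3 says that clinical decisions rest on the routine scans. These protect participants and add information, but none of them is a non-inferiority test of the primary outcome.

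**Conclusion.** The point holds in this form: the primary non-inferiority claim is tied to a rule with no margin and no confidence bound, and the only named test addresses a difference and is not connected to the conclusion. The two can point in opposite directions in the same data, as the 24-pair example shows (medians 4 and 4, p = 0.0016 against DLR). The simulated frequencies are illustrative only, because the number of Likert points and the score distribution are not in the protocol.

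The sample-size arithmetic is correct for a difference test. Whether 24 pairs per half suffice for non-inferiority cannot be settled from the protocol, which gives neither a margin nor an SD of paired differences. They give about 95% power only if the margin is about 0.8 SD or wider. This should be fixed before the first patient is scanned.

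**What to change.** - **Sections 4.2 and 5, endpoint.** Name one primary Likert item or summary score. Section 5 lists several: signal-to-noise, overall quality, four anatomical features, bowel motion and adequacy to report.
- **Sections 4.2 and 5, rule.** Have the radiologists fix and justify a margin on that score before the first patient. Declare non-inferiority only if the lower limit of the two-sided 95% confidence interval for the paired difference (DLR minus clinical) lies above the margin. The mean difference is one choice of estimate; the Hodges-Lehmann estimate serves if an ordinal method is preferred.
- **Reporting.** Give the percentages of patients scored worse, the same and better on DLR. Keep the Wilcoxon test for superiority, once non-inferiority is met.
- **Section 7.2.1.** Restate the power of 24 pairs per half for the chosen margin and an assumed SD. As a guide, a margin of half a point keeps 95% power only if the SD of paired differences is at most about 0.5/0.8 = 0.63 points.

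The cost is rewording, agreement on one endpoint and one margin, and possibly a less favourable stated power. If the sponsor wants 95% power at a tighter margin, more patients are needed: 100 at 0.6 SD and 143 at 0.5 SD, against 60 planned.

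### Secondary outcome b covers only the benefits of DLR, and no listed outcome reports how often a DLR series is not reportable when the clinical series is

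*Protocol*

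**What the plan says.** Section 4.2 of the protocol lists three outcomes:

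- Primary: equivalent image quality after a shorter acquisition, judged by "Median likert score DLR enabled >= clinical".
- Secondary a: "To show agreement between the clinically relevant measurements of rectal tumours on DLR enabled vs clinical scans".
- Secondary b: "To describe the potential benefits of using DLR enabled protocols, including shortened acquisition times and improved imaged quality".

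Section 5 describes the Likert form. Besides the scores for image quality and anatomy, it contains one overall item, "as well as an overall assessment of whether or not the radiologist agrees the image is of adequate quality to report". Patient images are assessed with "the same Likert scoring employed with the healthy volunteers". The only analysis named for the scores is a "two-tailed pairwise Wilcoxon signed-rank test". Section 5 then states that conclusions on image quality and "the validity of DLR being suitable for clinical rectum protocols will be made by" named investigators. It attaches no failure criterion to that conclusion.

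Section 1 explains why validation is needed: DLR algorithms are opaque, "where their failure modes are not well understood", and there are reports of abnormalities lost on deep-learning images.

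Section 7.2.1 allows a patient to be excluded after scanning because of marked movement in the DLR part only. It places such patients within the 20% dropout allowance.

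**The concern.** The risk that section 1 describes is occasional failure, but the outcome list looks at typical scores, measurement agreement and gains. A median and a signed-rank test describe the centre of the score distribution. Neither says what share of patients had a reportable clinical series and an unreportable DLR series.

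The judgement needed for that share is already on the form, yet no outcome uses it, and the one descriptive outcome is confined to benefits. A report that follows section 4.2 exactly could call DLR suitable without giving any failure frequency or bound on it. In a sample of this size, a run without failures would also look more reassuring than it is unless an interval is shown.

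**Working it through.** **Inputs.** From section 7.2.1: 24 pairs per half of the DLR protocol, dz 0.8, two-sided alpha 0.05, power 0.95, dropout 20%, 15 volunteers. The protocol does not state the length of the Likert scale. I assume 1 to 5, every clinical score at 4, and a DLR score of 1 for an image that cannot be reported.

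**1. The plan's own figures.** Noncentral t power for matched pairs, with n scaled by the Wilcoxon efficiency 3/π: 24 × 3/π = 22.9 effective pairs, giving power 0.955. The 24 reproduces. (24 × 2) ÷ (1 − 0.20) = 60 patients, and 60 + 15 = 75. That is 30 recruited and 24 evaluable patients per half.

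**2. What the median criterion tolerates.** Let k of the 24 DLR images score 1 and the rest 4. The median is the mean of the 12th and 13th ordered scores.
- k = 11: both are 4, so the median is 4 and the criterion is met with 11/24 = 46% at the lowest score.
- k = 12: (1 + 4)/2 = 2.5, and the criterion first fails.

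**3. What the signed-rank test tolerates.**
- Other DLR images unchanged at 4: only k differences are non-zero and all are negative, so p = 2 × 0.5^k. k = 5 (21%) gives 0.0625; k = 6 (25%) gives 0.031. The test first turns against DLR at 6 of 24.
- Other DLR images at 5, k = 3 (12.5%): 21 differences of +1 share rank 11, so R+ = 21 × 11 = 231. Three differences of −3 take ranks 22 to 24, so R− = 69. This gives p = 0.012 in favour of DLR.

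**4. What an adequacy count would show.** Exact (Clopper-Pearson) two-sided 95% limits. With no failures the upper limit is 1 − 0.025^(1/n).

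| Failures | n = 24 (one half) | n = 48 (both halves) |
|---|---|---|
| 0 | 0 to 14.2% | 0 to 7.4% |
| 1 | 0.1 to 21.1% | 0.1 to 11.1% |
| 3 | 2.7 to 32.4% | 1.3 to 17.2% |

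A true failure rate of 5% would produce no failure in 24 patients with probability 0.95^24 = 0.29.

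An exact McNemar test needs at least 6 discordant pairs, all in one direction, to reach p < 0.05 (2 × 0.5^6 = 0.031). The count with its interval is therefore the useful summary, and a test adds little.

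**5. Effect of the movement exclusion.** The dropout allowance is 60 × 0.20 = 12 patients, or 6 per half. The protocol does not say how many of these would be DLR-only movement, so take x from 0 to 6. If none of the 24 evaluable patients fails, the table shows 0/24 when such cases are dropped. If they are kept, the proportion is x/(24 + x), from 0 to 6/30 = 20%.

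**The case against.** Several objections carry weight.

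- **A statistical analysis plan could tabulate the item.** It could, and nothing in section 5 forbids it. A reader might infer that the protocol rules out reporting failures; the text does not go that far. But the outcome list is protocol content, and outcome b is worded there as benefits only.
- **The item may not be yes/no, and the pairing is inferred.** Both are correct. The item sits on a Likert form whose response format is not shown, and scoring of both series in each patient is inferred from the pairwise test. If the item is graded, a cut-off is needed.
- **The adequacy item does not capture the failure that section 1 describes.** A DLR image that omits an abnormality can look fully reportable. A reader might infer that the count would settle that risk. It would not; secondary outcome a touches it only in part, through measurements.
- **The design is not rigged for DLR.** The primary criterion can fail, the test is two-tailed, and measurements can disagree. A reader might infer that the whole report is biased; only outcome b is one-sided. The wording of the workflow decision recorded in Appendix 4 mentions Likert scores and biomarker analysis. The diagram itself is not shown, so its full content cannot be judged.
- **The limits in step 4 are not the size of an error.** They are the precision of hypothetical results. A reader might multiply an upper limit by the roughly 200 yearly referrals in section 6. That would present a bound as a patient count and apply a rate for half a protocol to whole examinations.

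**Conclusion.** The point stands in this form: outcome b is limited to benefits, and no listed outcome gives the frequency of DLR series that are inadequate to report when the clinical series is adequate, although that judgement is collected and a suitability conclusion follows.

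Under the assumed scale and scores, the median criterion tolerates up to 11 of 24 images at the lowest score, and the signed-rank test can favour DLR with 3 of 24. These figures illustrate how insensitive the criteria are; they do not predict results. With 24 pairs, even a clean half leaves an upper limit of 14.2%. No planned test is invalidated. What is missing is a summary that the suitability conclusion needs.

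**What to change.** Amend section 4.2 and the analysis text of section 5:

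1. Reword outcome b to describe both the benefits and the failures of DLR.
2. For each protocol half, report the number of patients with an adequate clinical series and an inadequate matching DLR series, and the reverse, with exact 95% confidence intervals. State that both series are scored for this item. If it is graded, fix the cut-off for not adequate before patient images are read.
3. Count patients with marked movement only in the DLR scan as DLR failures in this table, not as dropout. Show their number on a separate line: the DLR sequences are appended to the routine scan, so movement may reflect the longer session as well as the technique.
4. Quote the upper confidence limit in the suitability conclusion.
5. State that the count covers unreportable images only, and that abnormalities missed on adequate-looking DLR images are addressed only in part by secondary outcome a.

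The cost is a few sentences and one small table, with no extra patients, scan time or readers and no change to the 75. The drawback is that the report must show a wide interval.
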